3.3.1.1.1	Summary of Laboratory Values – Hematology by Age Group From Baseline to Week 52	Safety
3.3.1.2	Summary of Laboratory Values – Hematology in LTS Period	Safety
3.3.2.1	Summary of Laboratory Values – Chemistry From Baseline to Week 52	Safety
3.3.2.1.1	Summary of Laboratory Values – Chemistry by Age Group From Baseline to Week 52	Safety
3.3.2.2	Summary of Laboratory Values – Chemistry in LTS Period	Safety
3.3.3	Shift Summary of Hematology Laboratory Values in CTC Grade – To the Worst Abnormal Value From Baseline to Week 8	Safety
3.3.4	Shift Summary of Chemistry Laboratory Values in CTC Grade – To the Worst Abnormal Value From Baseline to Week 8	Safety
3.3.5	Shift Summary of Hematology Values – To the Worst Abnormal Value	Safety
3.3.6	Shift Summary of Chemistry Values – To the Worst Abnormal Value	Safety
Vital Signs		
3.4.1.1	Summary of Systolic Blood Pressure From Baseline to Week 52	Safety
3.4.1.2	Summary of Systolic Blood Pressure in LTS Period	Safety
3.4.2.1	Summary of Diastolic Blood Pressure From Baseline to Week 52	Safety
3.4.2.2	Summary of Diastolic Blood Pressure in LTS Period	Safety
3.4.3.1	Summary of Pulse From Baseline to Week 52	Safety
3.4.3.2	Summary of Pulse in LTS Period	Safety
3.4.4.1	Summary of Respiratory Rate From Baseline to Week 52	Safety
3.4.4.2	Summary of Respiratory Rate in LTS Period	Safety
3.4.5.1	Summary of Body Temperature From Baseline to Week 52	Safety
3.4.5.2	Summary of Body Temperature in LTS Period	Safety

Figure

Figure No.	Title	Population
4.1	Proportion of Participants Achieving IGA-TS From Baseline to Week 52	ITT
4.2.1	Proportion of Participants Achieving EASI75 in VC Period	ITT
4.2.2.1	Mean and Standard Error Plot of EASI Score in VC Period	ITT
4.2.2.2	Mean and Standard Error Plot of Change From Baseline in EASI Score in VC Period	ITT
4.2.2.3	Mean and Standard Error Plot of Percent Change From Baseline in EASI Score in VC Period	ITT
4.3.1	Proportion of Participants Achieving \geq 4-point Improvement in Itch NRS Score in VC Period	ITT
4.3.2.1	Mean and Standard Error Plot of Itch NRS Score in VC Period	ITT
4.3.2.2	Mean and Standard Error Plot of Change From Baseline in Itch NRS Score in VC Period	ITT
4.3.2.3	Mean and Standard Error Plot of Percent Change From Baseline in Itch NRS Score in VC Period	ITT

Figure No.	Title	Population
4.3.3.1	Mean and Standard Error Plot of Daily Itch NRS Score in VC Period	ITT
4.3.3.2	Mean and Standard Error Plot of Change From Baseline in Daily Itch NRS Score in VC Period	ITT
4.3.3.3	Mean and Standard Error Plot of Percent Change From Baseline in Daily Itch NRS Score in VC Period	ITT
4.3.4.1	Kaplan-Meier Curve of the Time to \geq 2-Point Improvement in Itch NRS Score in VC Period	ITT
4.3.4.2	Kaplan-Meier Curve of the Time to \geq 3-Point Improvement in Itch NRS Score in VC Period	ITT
4.3.4.3	Kaplan-Meier Curve of the Time to \geq 4-Point Improvement in Itch NRS Score in VC Period	ITT
4.4.1	Proportion of Participants Achieving a \geq 6-Point Improvement in the PROMIS Sleep Disturbance Score (8b) From Baseline to Week 52	ITT
4.4.2.1	Mean and Standard Error Plot of PROMIS Sleep Disturbance Score (8b) From Baseline to Week 52	ITT
4.4.2.2	Mean and Standard Error Plot of Change From Baseline in PROMIS Sleep Disturbance Score (8b) From Baseline to Week 52	ITT
4.4.2.3	Mean and Standard Error Plot of Percentage Change From Baseline in PROMIS Sleep Disturbance Score (8b) From Baseline to Week 52	ITT
4.4.3.1	Mean and Standard Error Plot of Daily PROMIS Sleep Disturbance Score (8b) From Baseline to Week 52	ITT
4.4.3.2	Mean and Standard Error Plot of Change From Baseline in Daily PROMIS Sleep Disturbance Score (8b) From Baseline to Week 52	ITT
4.4.3.3	Mean and Standard Error Plot of Percent Change From Baseline in Daily PROMIS Sleep Disturbance Score (8b) From Baseline to Week 52	ITT
4.5.1	Proportion of Participants Achieving a \geq 6-point Improvement in the PROMIS Sleep-Related Impairment (8a) From Baseline to Week 52	ITT
4.5.2.1	Mean and Standard Error Plot of PROMIS Sleep-Related Impairment (8a) From Baseline to Week 52	ITT
4.5.2.2	Mean and Standard Error Plot of Change From Baseline in PROMIS Sleep-Related Impairment (8a) From Baseline to Week 52	ITT
4.5.2.3	Mean and Standard Error Plot of Percentage Change From Baseline in PROMIS Sleep-Related Impairment (8a) From Baseline to Week 52	ITT
4.5.3.1	Mean and Standard Error Plot of Daily PROMIS Sleep-Related Impairment (8a) From Baseline to Week 52	ITT
4.5.3.2	Mean and Standard Error Plot of Change From Baseline in Daily PROMIS Sleep-Related Impairment (8a) From Baseline to Week 52	ITT
4.5.3.3	Mean and Standard Error Plot of Percent Change From Baseline in Daily PROMIS Sleep-Related Impairment (8a) From Baseline to Week 52	ITT
4.6	Kaplan-Meier Curve of the Time to First Retreatment in LTS Period	ITT

Listings

Listing No.	Title
Baseline Demographic and Characteristic	
2.1.1	Participant Enrollment and Disposition Status
2.1.2	Participant Inclusion and Exclusion Criteria Violations

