Inclusion/exclusion criteria review	X	X				
Demography and general and disease medical history	X					
Prior/concomitant medications	X	X	X	X	X	
Apply study drug		X	X	X	X	1st AM application under site supervision.
Weigh/dispense or re-dispense study drug and distribute study drug diary and reminder card		X	X	X	X	Used tubes will be replenished, and unused tubes may be re-dispensed.
Collect/weigh study drug and collect/review study drug diary			X	X	X	
Assess compliance		X	X	X	X	
Safety assessments						
AE assessments and targeted physical examinations	X	X	X	X	X	Body systems with symptoms should be physically examined. Ad hoc photography of skin-related AEs should also occur as applicable.
Comprehensive physical examination	X				X	
Vital signs/body weight/height	X*	X	X	X	X*	*Height and weight at screening and Week 8.
12-lead ECG	X					12-lead ECG performed within 2 months before baseline is acceptable.

Table 3: Schedule of Activities: Vehicle-Controlled Period (Continued)

Visit Day (Range)	Screening	Vehicle-Controlled Treatment				Notes
	Days -28 to -1	Day 1 (Baseline)	Week 2 (± 3 d)	Week 4 (± 3 d)	Week 8*/EOT (± 3 d)	
Efficacy assessments						
Evaluate %BSA affected by active AD	X	X	X	X	X*	*At Week 8, to qualify for LTS period, the %BSA range is 0% to ≤ 20%.
Target lesion	X	X*	X	X	X	*A lesion of ≥ 10 cm ² needs to be identified at baseline (excluding the hands, feet and genitalia)
Photography (target lesion close-up/ regional body area)		X	X	X	X	Ad hoc photography (at selected sites) of skin-related AEs is recommended.
EASI	X	X	X	X	X	
SCORAD		X	X	X	X	
IGA	X	X	X	X	X*	*At Week 8, to qualify for LTS period, the IGA range is 0 to 4.
Itch NRS	Diary is completed each evening from screening through the last application of study drug in the vehicle-controlled period.					
Skin Pain NRS						
Patient-reported outcome questionnaires – to be evaluated prior to any other study procedures/assessments; see Section 8.2.7						
DLQI/CDLQI		X	X	X	X	
PGIC			X	X	X	
POEM		X	X	X	X	
EQ-5D-5L questionnaire	X	X	X	X	X	
WPAI:SHP questionnaire	X	X	X	X	X	
PROMIS sleep questionnaires (24-hour recall)	Diary is completed daily from screening through the last application of study drug in the vehicle-controlled period.					PROMIS Short Form – Sleep-Related Impairment (8a) collected in the evening before sleeping. PROMIS Short Form – Sleep Disturbance (8b) collected in the morning after the participant wakes up.
PROMIS sleep questionnaires (7-day recall)					X	

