Table 4: Schedule of Activities: Long-Term Safety Extension Period (Continued)

Visit Day (Range)	LTS Extension Treatment						Follow-Up	Notes
	Week 12 (±7 d)	Weeks 16, 20, and 24 (±7 d)	Weeks 28, 32, and 36 (±7 d)	Weeks 40, 44, and 48 (±7 d)	Week 52 ET/EOT (±7 d)	Unscheduled Visits		
Patient-reported outcome questionnaires – to be evaluated prior to any other study procedures/assessments; see Section 8.2.7								
DLQI/CDLQI	X	X*			X	X	X	*At Week 24 only.
POEM	X	X*			X	X	X	*At Week 24 only.
EQ-5D-5L questionnaire	X	X*	X*		X		X	*At Weeks 24 and 36 only
WPAI:SHP questionnaire	X	X*	X*		X		X	*At Weeks 24 and 36 only.
PROMIS sleep questionnaires (7-day recall)	X	X*			X			*At Week 24 only. PROMIS Short Form – Sleep-Related Impairment (8a). PROMIS Short Form – Sleep Disturbance (8b). Note: Recall period changed from past 24 hours to past 7 days during LTS period.
Laboratory assessments	Blood draw for clinical laboratory tests must be performed before the in-clinic study drug application.							
Serum chemistries	X	X	X	X	X	X	X	
Hematology	X	X	X	X	X	X	X	
Pregnancy testing	X	X	X	X	X	X	X*	*Female participants of childbearing potential will have a serum test at screening and follow-up and a urine test at all other visits. A positive urine test must be confirmed by a serum test.
PK plasma sampling (trough)	X	X	X	X	X	X	X	Time of last study drug application to be written in eCRF. Blood samples must not be drawn from the area that has been treated with study drug.

CONFIDENTIAL

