7.3.1.2. PROMIS Short Form – Sleep Disturbance (8b)

The PROMIS Short Form – Sleep Disturbance (8b) is an 8-item questionnaire. Each item on the measure is rated on a 5-point scale with a range in score from 8 to 40 with higher scores indicating greater severity of sleep disturbance. The recall period will be the past 24 hours for the VC period and the past 7 days for the LTS period. The raw scores on the 8 items should be summed to obtain a total raw score. If 4 or more of the total items on the measure are missing for a given day/assessment, the scores should not be used.

For total raw score, the baseline will be determined by averaging the 7 daily scores on and before Day 1 (Day -6 to Day 1). The by-visit score for post-baseline visits will be determined by averaging the 7 daily scores before the visit day. If 4 or more daily scores are missing (out of the 7), the by-visit score at the visit will be set to missing.

Clinically meaningful difference is defined as a ≥ 6 -point change over baseline. The total raw score will be summarized by visit and by treatment. The proportion of participants with a ≥ 6 -point improvement in the PROMIS Short Form – Sleep Disturbance (8b – 24-hour recall) score will be summarized by treatment group for participants with baseline ≥ 6 .

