7.3.1.3. PROMIS Short Form – Sleep-Related Impairment (8a)

The PROMIS Short Form – Sleep-Related Impairment (8a) is an 8-item questionnaire. Each item on the measure is rated on a 5-point scale (1 = Not at all; 2 = A little bit; 3 = Somewhat; 4 = Quite a bit; and 5 = Very much) with a range in score from 8 to 40 with higher scores indicating greater severity of sleep-related impairment. The recall period will be the past 24 hours for the VC period and the past 7 days for the LTS period. The raw scores on the 8 items should be summed to obtain a total raw score. If 4 or more of the total items on the measure are missing, the scores should not be used.

For total raw score, the baseline will be determined by averaging the 7 daily scores before Day 1 (Day -7 to Day -1). The by-visit score for post-baseline VC visits will be determined by averaging the 7 daily scores before the visit day. If 4 or more daily scores are missing (out of the 7), the by-visit score at the visit will be set to missing.

Clinical meaningful difference is defined as a \geq 6-point change over baseline. The total raw score will be summarized by visit and by treatment. The proportion of participants with a \geq 6-point (clinically meaningful) improvement in the PROMIS Short Form – Sleep-Related Impairment (8a – 24-hour recall) score will be summarized by treatment group for participants with baseline \geq 6.

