2.1.10.2	Summary of Participants in Each Category of IGA Score in LTS Period	ITT
2.1.11.1	Summary and Analysis of Participants Achieving an IGA of 0 or 1 From Baseline to Week 52	ITT
2.1.11.2	Summary of Participants Achieving an IGA of 0 or 1 in LTS Period	ITT
2.1.12	Shift Summary of IGA at Week 8	ITT
EASI		
2.2.1	Summary and Analysis of Participants Achieving EASI75 in VC Period	ITT
2.2.2	Summary and Analysis of Participants Achieving EASI50 in VC Period	ITT
2.2.3	Summary and Analysis of Participants Achieving EASI90 in VC Period	ITT
2.2.4	Summary and Analysis of EASI Score in VC Period	ITT
2.2.5	Summary of Participants in Each Category of EASI Score in VC Period	ITT
Itch NRS Score		
2.3.1	Summary and Analysis of Participants Achieving \geq 2-Point Improvement in Itch NRS Score in VC Period	ITT
2.3.2	Summary and Analysis of Participants With a \geq 3-Point Improvement in Itch NRS Score in VC Period	ITT
2.3.3	Summary and Analysis of Participants With a \geq 4-Point Improvement in Itch NRS Score in VC Period	ITT
2.3.4	Summary and Analysis of Itch NRS Score in VC Period	ITT
2.3.5	Summary and Analysis of Daily Itch NRS Score in VC Period	ITT
2.3.6	Summary and Analysis of Time to \geq 2-Point Improvement in Itch NRS Score in VC Period	ITT
2.3.7	Summary and Analysis of Time to \geq 3-Point Improvement in Itch NRS Score in VC Period	ITT
2.3.8	Summary and Analysis of Time to \geq 4-Point Improvement in Itch NRS Score in VC Period	ITT
PROMIS Sleep Disturbance Score (8b)		
2.4.1.1	Summary and Analysis of Participants Achieving a \geq 6-point Improvement in the PROMIS Sleep Disturbance Score (8b) From Baseline to Week 52	ITT
2.4.1.2	Summary of Participants Achieving a \geq 6-point Improvement in the PROMIS Sleep Disturbance Score (8b) in LTS Period	ITT
2.4.2.1	Summary and Analysis of By-Visit PROMIS Sleep Disturbance Score (8b) From Baseline to Week 52	ITT
2.4.2.2	Summary of By-Visit PROMIS Sleep Disturbance Score (8b) in LTS Period	ITT
2.4.3	Summary and Analysis of Daily PROMIS Sleep Disturbance Score (8b) in VC Period	ITT
PROMIS Sleep-Related Impairment Score (8a)		
2.5.1.1	Summary and Analysis of Participants Achieving a \geq 6-point Improvement in the PROMIS Sleep-Related Impairment Score (8a) From Baseline to Week 52	ITT
2.5.1.2	Summary of Participants Achieving a \geq 6-point Improvement in the PROMIS Sleep-Related Impairment Score (8a) in LTS Period	ITT

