2.5.2.1	Summary and Analysis of By-Visit PROMIS Sleep-Related Impairment Score (8a) From Baseline to Week 52	ITT

Table No.	Title	Population
2.5.2.2	Summary of By-Visit PROMIS Sleep-Related Impairment Score (8a) in LTS Period	ITT
2.5.3	Summary and Analysis of Daily PROMIS Sleep-Related Impairment Score (8a) in VC Period	ITT
SCORAD		
2.6	Summary and Analysis of SCORAD Score in VC Period	ITT
Skin Pain NRS Score		
2.7.1	Summary and Analysis of By-Visit Skin Pain NRS Score in VC Period	ITT
2.7.2	Summary and Analysis of Daily Skin Pain NRS Score in VC Period	ITT
BSA		
2.8.1.1	Summary and Analysis of Total %BSA Afflicted by AD From Baseline to Week 52	ITT
2.8.1.2	Summary of Total %BSA Afflicted by AD in LTS Period	ITT
POEM		
2.9.1.1	Summary and Analysis of Total POEM Score From Baseline to Week 52	ITT
2.9.1.2	Summary of Total POEM Score in LTS Period	ITT
2.9.2.1	Summary of Participants in Each Category of POEM Score From Baseline to Week 52	ITT
2.9.2.2	Summary of Participants in Each Category of POEM Score in LTS Period	ITT
DLQI/CDLQI		
2.10.1.1	Summary and Analysis of Total DLQI Score From Baseline to Week 52	ITT
2.10.1.2	Summary and Analysis of Total CDLQI Score From Baseline to Week 52	ITT
2.10.1.3	Summary of Total DLQI Score in LTS Period	ITT
2.10.1.4	Summary of Total CDLQI Score in LTS Period	ITT
2.10.2.1	Summary and Analysis of DLQI Subscore From Baseline to Week 52	ITT
2.10.2.2	Summary and Analysis of CDLQI Subscore From Baseline to Week 52	ITT
2.10.2.3	Summary of DLQI Subscore in LTS Period	ITT
2.10.2.4	Summary of CDLQI Subscore in LTS Period	ITT
2.10.3.1	Summary of Participants in Each Category of DLQI Score From Baseline to Week 52	ITT
2.10.3.2	Summary of Participants in Each Category of CDLQI Score From Baseline to Week 52	ITT
2.10.3.3	Summary of Participants in Each Category of DLQI Score in LTS Period	ITT
2.10.3.4	Summary of Participants in Each Category of CDLQI Score in LTS Period	ITT
2.10.4.1	Summary and Analysis of Participants Achieving ≥ 4 Improvement in DLQI Score From Baseline to Week 52	ITT
2.10.4.2	Summary and Analysis of Participants Achieving ≥ 4 Improvement in CDLQI Score From Baseline to Week 52	ITT
2.10.4.3	Summary of Participants Achieving ≥ 4 Improvement in DLQI Score in LTS Period	ITT
2.10.4.4	Summary of Participants Achieving ≥ 4 Improvement in CDLQI Score in LTS Period	ITT
PGIC		
2.11.1	Summary and Analysis of Participants Achieving a PGIC Score of 1 or 2 in VC Period	ITT

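### PROMIS sleep outputs running to Week 52 set 7-day-recall LTS scores against a 24-hour-recall diary baseline, so descriptive within-arm change after Week 8 mixes treatment effect with a change of measurement

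*SAP*

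**What the plan says.** **Measurement.** Both sleep forms (8b Sleep Disturbance, 8a Sleep-Related Impairment) are completed daily by diary until the VC period ends. SAP 7.3.1.2 states for 8b: "The recall period will be the past 24 hours for the VC period and the past 7 days for the LTS period". SAP 7.3.1.3 says the same for 8a, and Protocol Table 4 carries the remark "Note: Recall period changed from past 24 hours to past 7 days during LTS period". In Protocol Table 3 the 7-day form is marked at Week 8 and at no other VC visit. Protocol 8.2.7 treats that Week 8 assessment as the LTS baseline. Table 4 repeats the form at Weeks 12, 24 and 52. Protocol 8.2.7.8 moves collection from diary to site tablet.

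**Baseline.** For 8b (SAP 7.3.1.2), "the baseline will be determined by averaging the 7 daily scores on and before Day 1 (Day -6 to Day 1"). For 8a (SAP 7.3.1.3), "the baseline will be determined by averaging the 7 daily scores before Day 1 (Day -7 to Day -1"). Both are means of 24-hour-recall diary scores.

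**Endpoints.** SAP Table 1 ties the 6-point responder and change endpoints to the 24-hour score at Weeks 2, 4 and 8. For the 7-day version it lists only the score, at Weeks 8, 12, 24 and 52.

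**Outputs.** Appendix A nevertheless plans these displays from baseline to Week 52:

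- 6-point responder Tables 2.4.1.1 and 2.5.1.1, and Figures 4.4.1 and 4.5.1;
- by-visit Tables 2.4.2.1 ("Summary and Analysis of By-Visit PROMIS Sleep Disturbance Score (8b) From Baseline to Week 52") and 2.5.2.1 ("Summary and Analysis of By-Visit PROMIS Sleep-Related Impairment Score (8a) From Baseline to Week 52");
- Figures 4.4.2.2 and 4.5.2.2 (change from baseline), and 4.4.2.3 and 4.5.2.3 (percentage change).

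**The concern.** A change from baseline needs the same measure at both ends. Here three things change together after Week 8: the recall period, the mode of collection, and the aggregation (a mean of seven daily scores becomes one questionnaire). If the 7-day version reads systematically higher or lower than the diary mean for the same week, the displays will show sleep benefit lost or gained between Week 8 and Week 12 when nothing has happened to the participant. There is no vehicle arm after Week 8 to reveal this. These are the outputs a reader would use to judge whether the sleep benefit lasts to one year.

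**Working it through.** The plan states no figure on this point, so there is nothing to reproduce. The check sets the scheduled data beside the planned outputs and then shows how sensitive the responder rate would be.

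**Step 1. Which PROMIS scores exist at each time** (Protocol Tables 3 and 4, Sections 8.2.7 and 8.2.7.8; SAP 7.3.1.2 and 7.3.1.3)

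| Time | 24-hour diary mean | 7-day tablet score |
|---|---|---|
| Before treatment | yes | no |
| Weeks 2 and 4 | yes | no |
| Week 8 | yes | yes |
| Weeks 12, 24 and 52 | no | yes |

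No time after Week 8 shares a version with the pre-treatment baseline. For a participant who stays on the same active cream, a post-Week 8 change from baseline can only be a 7-day score set against a 24-hour baseline.

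**Step 2. Whether the planned outputs contain that change.** Figures 4.4.2.2, 4.4.2.3, 4.5.2.2 and 4.5.2.3 name change or percentage change in their titles and run to Week 52, so they are the most direct evidence. The responder tables and Figures 4.4.1 and 4.5.1 need a change in order to classify anyone. Tables 2.4.2.1 and 2.5.2.1 are titled by score only. They are drawn in because SAP 7.1 calls for change as well as the actual value where available, and SAP 7.4.2.1 includes change and percentage change in the by-visit PROMIS summaries.

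**Step 3. Whether any rule bridges the versions.** None was found. The 8b by-visit rule averages the seven daily scores before the visit, which cannot be done at an LTS visit because the diary has stopped. SAP 7.3.1.3 limits the matching 8a rule to VC visits; SAP 7.3.1.2 does not limit the 8b rule.

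**Step 4. What the displayed quantity is.** Let D0 be the baseline diary mean, W the 7-day score at an LTS visit, D the diary mean that would have been recorded for that same week, and b = W − D. Then

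displayed improvement = D0 − W = (D0 − D) − b.

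A 6-point response on the displayed scale therefore requires an improvement of at least 6 + b on the diary scale.

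**Step 5. Sensitivity, under assumptions that are not in the documents.** Take improvement on the diary scale as normal with mean m and SD s. The responder rate is 1 − Φ((6 − m + b)/s). For m = 4, s = 6 and b = 1 this is 1 − Φ(3/6) = 30.9%, against 1 − Φ(2/6) = 36.9% with no shift.

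| m, s | b = −2 | b = −1 | b = 0 | b = 1 | b = 2 |
|---|---|---|---|---|---|
| 2, 6 | 36.9% | 30.9% | 25.2% | 20.2% | 15.9% |
| 2, 8 | 40.1% | 35.4% | 30.9% | 26.6% | 22.7% |
| 4, 6 | 50.0% | 43.4% | 36.9% | 30.9% | 25.2% |
| 4, 8 | 50.0% | 45.0% | 40.1% | 35.4% | 30.9% |

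Across these rows a 1-point shift moves the rate by 4.3 (30.9 − 26.6) to 6.5 (43.4 − 36.9) percentage points. A 2-point shift moves it by 8.2 (30.9 − 22.7) to 13.1 (50.0 − 36.9).

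**The case against.** The SAP never writes the subtraction out; it is inferred from output titles and the schedule. The body of the SAP points the other way: Table 1 and Sections 7.4.2.1 and 7.4.2.3 label the change and responder measures as 24-hour recall, and the 7-day endpoint is a score only. The introduction to Appendix A calls the list and shells a guideline, and the sample displays are in a separate document that is not available here. The two versions share the same eight items and the same 8 to 40 range, and the baseline also spans a week, so b could be close to zero. LTS continuous data get summary statistics only, and a shift common to both active arms would largely cancel in a comparison of their mean changes.

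Much of this stands as a limit on size and consequence. It does not remove the point. The four change figures name change through Week 52, and no same-version baseline exists from which to draw them. The Appendix A exemption covers only modifications that leave the nature of the analysis alone, and the choice of baseline and recall version does not. If the intention was to stop at Week 8, the titles are wrong and still need correcting. Cancellation between arms does not help a within-arm statement about durability.

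A reader might also infer that every PROMIS table and every LTS column is wrong. The documents do not support that:

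- Tables 2.4.3 and 2.5.3 are daily and confined to the VC period.
- In the tables restricted to the LTS period (2.4.1.2, 2.4.2.2, 2.5.1.2, 2.5.2.2) the baseline version is unstated rather than clearly mismatched. SAP 4.1.3 resets the baseline at LTS entry for participants crossing over from vehicle. Both versions exist at Week 8, so a 7-day-to-7-day change is possible for them; the SAP does not say which version applies.
- Titles such as "Mean and Standard Error Plot of Daily PROMIS Sleep-Related Impairment (8a) From Baseline to Week 52" promise daily data where none are collected. That is a title slip, since the companion tables stop at the VC period. It is not evidence of mixed recall.

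**Conclusion.** The point holds for Tables 2.4.1.1, 2.4.2.1, 2.5.1.1 and 2.5.2.1, Figures 4.4.1 and 4.5.1, and most directly Figures 4.4.2.2, 4.4.2.3, 4.5.2.2 and 4.5.2.3. For participants who stay on active drug, the descriptive within-arm LTS change and 6-point responder rate cannot be separated from the change of recall period, mode and aggregation.

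The size is unknown. The documents give neither the magnitude nor the direction of b, and the rates in the working rest on assumed normal changes with assumed means and SDs. They show only that a shift of a point or two would be visible in a responder plot.

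A reader might go further and infer that the key secondary sleep results are compromised. They are not: H14, H24, H31 and H32 are Week 8 comparisons using 24-hour scores at both ends. The matter is worth correcting because it bears on any claim of lasting sleep benefit and costs almost nothing to put right, not because a confirmatory result is at risk.

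**What to change.** 1. End the 24-hour-recall change, percentage-change and 6-point responder outputs at Week 8, in line with SAP Table 1.
2. For Weeks 12, 24 and 52, present the 7-day-recall score and its change from the Week 8 7-day-recall score.
3. State in SAP 4.1.3 or 7.3.1 that the Week 8 7-day score is the PROMIS LTS baseline for crossover participants, and apply it in the LTS-period tables.
4. Report the paired Week 8 difference between the 7-day score and the diary mean, by treatment group. This estimates b directly from scheduled data.
5. Put the recall period in the title of every PROMIS table and figure.
6. As a clerical correction only, retitle Figures 4.4.3.x and 4.5.3.x to the VC period.

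The cost is SAP wording, titles and shells; no new data are needed. The one small loss is that LTS outputs would no longer show change from the pre-treatment baseline. The paired Week 8 comparison lets a reader judge how far the two series can be read together.
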